5.5. Other Secondary Endpoint(s)

Statistical analyses will be descriptive and exploratory only. They will be performed for the Intent-to-treat analysis set and, if requested, the Per-protocol analysis set. Details on handling of missing data are described in section 5.1.8.

Other secondary endpoints of this study to be evaluated in Study Part 3 are:

- Proportion of subjects who achieve a PASI 75/90/100 response at weeks 116, 164, and 220, per study group
- Time to loss of disease control (absolute PASI score >5 at any visit) after treatment withdrawal beyond week 68 per study group
- Change from baseline (week 0) in Dermatology Life Quality Index (DLQI) score at weeks 116, 164, and 220, per study group
- Proportion of subjects who achieve a DLQI score 0/1 and <5 at weeks 116, 164, and 220, per study group
- Change from baseline (week 0) in affected Body Surface Area (BSA) at weeks 80, 104, 116, 140, 164, 188, 212, and 220
- Change from baseline (week 0) in the Nail Assessment in Psoriasis and Psoriatic Arthritis (NAPPA) score at weeks 116, 164, and 220, among subjects with nail psoriasis at baseline (week 0)
- Change from baseline (week 0) in the signs and symptoms aggregate scores of the Psoriasis Symptoms and Signs Diary (PSSD) at weeks 116, 164, and 220.

5.5.1. Definition of Endpoint(s)

5.5.1.1. Psoriasis Area and Severity Index (PASI)

Efficacy endpoints related to the PASI score are defined below:

PASI 75 Responder

Subjects with $\geq 75\%$ improvement in PASI from baseline will be considered PASI 75 responders.

PASI 90 Responder

Subjects with $\geq 90\%$ improvement in PASI from baseline will be considered PASI 90 responders.

PASI 100 Responder

Subjects with a PASI score of 0 will be considered PASI 100 responders.

Time to loss of disease control

The time to loss of disease control is defined as time from the week 68 visit (start of withdrawal phase) to first date PASI is >5 within Study Part 3. In the absence of documented disease control, the time to loss of disease control will be censored at the date of the last PASI assessment until the week 116/164/220 visit. The time to loss of disease control will be computed as:

- Date of PASI >5 – Date of week 68, if the subject loses disease control,
- Date of last PASI assessment – Date of week 68, if the subject maintains disease control.
- In case the subject missed the week 68 visit, the start date of the withdrawal phase will be estimated as 8 weeks (56 days) after the week 60 visit.

5.5.1.2. Dermatology Life Quality Index (DLQI)

The Dermatology Life Quality Index (DLQI) is a dermatology-specific quality of life instrument designed to assess the impact of the disease on a subject's quality of life. It is a 10-item questionnaire that, in addition to evaluating overall quality of life, can be used to assess 6 different aspects that may affect quality of life: 1) symptoms and feelings, 2) daily activities, 3) leisure, 4) work or school performance, 5) personal relationships, and 6) treatment.

The DLQI is calculated by summing the score of each question resulting in a maximum of 30 and a minimum of 0. A higher score indicates more severe disease. A score of ≤ 1 indicates no effect at all of disease on subject's health related quality of life.

For a partially answered questionnaire (eg, not all 10 answers in the DLQI questionnaire are available) the following rules will be applied:

1. If one question is left unanswered this will be scored 0 and the scores will be summed and expressed as usual out of a maximum of 30.
2. If two or more questions are left unanswered the questionnaire will not be scored.
3. If question 7 is answered 'yes' this will be scored 3. If question 7 is answered 'no' or 'not relevant' but then either 'a lot' or 'a little' is ticked this will be scored 2 or 1. If it is answered 'no', but the second half is left incomplete, the score will remain 0.

Note: The answer "Not relevant" will be scored 0, as intended by the score developers.

5.5.1.3. Body Surface Area (BSA%)

One physical measure to define disease severity is to determine how much of the Body Surface Area (BSA) is affected by psoriasis. Involved BSA is calculated by using the palm of the subject's hand as equivalent to 1% of the BSA (rule of palm).

5.5.1.4. Nail Assessment in Psoriasis and Psoriatic Arthritis (NAPPA)

The NAPPA is an instrument for assessing clinical and patient-reported outcomes in nail psoriasis (Augustin, et al. 2014). It comprises three components:

1. NAPPA-QOL is a 20-item nail-specific quality of life (QoL) questionnaire covering the past week. Signs, stigma and everyday life are rated on a scale from 0 (no suffering) to 4 (high suffering). The NAPPA-QOL global score is computed by averaging all items. In case more than 25% of the items are missing (6 or more items missing), the score is not computed for the respective patient.
2. NAPPA-PBI is a 24-item questionnaire to assess patient-defined needs before and patient-rated benefits after treatment. The answers are given on a scale from 0 to 4. The weighted NAPPA-PBI global score is computed as follows: For score calculation, both "does not apply" and "question unanswered" will be treated as missing values. The global score will be calculated using all items pairs (importance + benefit) for which the patient has given a response other than "does not apply". Each benefit item is multiplied with the respective

importance item, and the product is divided by the sum of all importance items. The results are summed up over all items. The resulting global score ranges from 0 (no benefit) to 4 (highest possible benefit). Only if more than 25% of items pairs are unanswered (=7 or more item pairs with missing values), no global score will be calculated.

3. NAPPA-CLIN has been developed from the Nail Psoriasis Severity Index (NAPSI) score, a nail psoriasis-specific score, which in its original version comprises the assessment of matrix and nail bed involvement in every finger and toe by 8 criteria for each nail. The NAPPA-CLIN is a simplified version of the NAPSI which only assesses the least and the worst involved nail of both hands, or both feet, respectively. Score (matrix or bed for hands or feet) is 0 if the findings are not present, 1 if they are present in 1 quadrant of the nail, 2 if present in 2 quadrants of a nail, 3 if present in 3 quadrants of a nail, and 4 if present in 4 quadrants of a nail:
 - thus, each nail has a matrix score (0-4) and a nail bed score (0-4), and the total nail score is the sum of those 2 individual scores (0-8) for hands or feet;
 - sum of the total score of all involved nails is the total NAPPA-CLIN score for that patient at that time for hands or feet;
 - thus, the NAPPA-CLIN scores for hands or feet range from 0 to 16 empirically;
 - if a matrix score or a nail bed score is missing, the NAPPA-CLIN score is also missing.

5.5.1.5. Psoriasis Symptom and Sign Diary (PSSD)

The Psoriasis Symptom and Sign Diary (PSSD) is a patient-reported outcome (PRO) questionnaire designed to measure the severity of psoriasis symptoms and signs for the assessment of treatment benefit. The PSSD includes 11 items covering symptoms (itch, pain, stinging, burning and skin tightness) and subject observable signs (skin dryness, cracking, scaling, shedding or flaking, redness and bleeding) using 0 (=absent) to 10 (=worst imaginable) numerical rating scales for severity. Two subscores will be derived: the psoriasis symptom score and the psoriasis sign score. A higher score indicates more severe disease. Additionally, the single items itch, pain, and scaling and also the other single items will be evaluated. The subjects will complete the 7-day recall version of the PSSD as indicated in the Time and Events Schedule.

The calculations of PSSD symptom, and sign scores are listed below.

Symptom Score (0-100)

- a) Symptom score includes itch (Q1), pain (Q11), stinging (Q10), burning (Q9) and skin tightness (Q4).
- b) Averaging items on the symptom scores when at least 3 items ($\geq 50\%$ of 5 items) on this scale are answered. Then, the average value is converted into 0-100 scoring such that Symptom score = average value x 10 with 0 representing the least severe and 100 the most severe. Otherwise, the symptom score will be set to missing.

Sign Score (0-100)

- a) Sign score includes skin dryness (Q2), cracking (Q3), scaling (Q5), shedding or flaking (Q6), redness (Q7) and bleeding (Q8).
- b) Averaging items on the sign scores when at least 3 items ($\geq 50\%$ of 6 items) on this scale are answered. Then, the average value is converted into 0-100 scoring such that Sign score = average value x 10 with 0 representing the least severe and 100 the most severe. Otherwise, the sign score will be set to missing.

5.5.2. Estimand(s)

NA

5.5.3. Analysis Methods

5.5.3.1. Psoriasis Area and Severity Index (PASI)

- Proportion of subjects who achieve a PASI 75/90/100 response at weeks 116, 164, and 220

The proportion of subjects still meeting the response criteria will be displayed in frequency tables providing the number and percentage of subjects per study group (NRI and OC analysis) along with odds ratio (OR), relative risk (RR) and risk difference (RD), and two-sided Wald-type 95% confidence intervals (95% CIs) stratified by 'disease duration'. For single proportions within each study group, unstratified two-sided 95% CIs according to Clopper-Pearson will be calculated. Graphical presentation will be presented by means of bar charts.

The two-group large-sample normal approximation Wald Z-test with Mantel-Haenszel stratum weights for 'disease duration' will be used to compare the proportion of responding subjects among the study groups. The Mantel-Haenszel estimate, the two-sided Wald-type 95% confidence limits, and the test for the difference of proportions will be computed by using Mantel-Haenszel stratum weights (Mantel & Haenszel, 1959) and the Sato variance estimator (Sato 1989).

Results will also be given for the entire population. In addition, in a modified OC analysis all subjects fulfilling the criteria for re-treatment within the week 116 visit window (ie, PASI>5) will be disregarded.

- Time to loss of disease control after treatment withdrawal beyond week 68

Time-to-event endpoints will be analyzed using the Kaplan-Meier product limit method and Cox proportional hazards model. Summary tables will provide counts and percentages by study group, the median time-to-event with 95% confidence intervals (CI), and the hazard ratio (including 95% CI and the p-value calculated from Cox-regression with the factors 'study group' and 'disease duration'). The survival curves will also be displayed graphically. Time-to-event analyses of binary endpoints will be performed on the observed cases only after the rule for handling of protocol-prohibited medication/therapy is applied. (ie, missing data will not be replaced for time-to-event analyses).

Time to loss of disease control will also be evaluated by disease duration category (assessed at baseline, ie, ≤ 2 years, >2 years, <15 months, 15 to 24 months) and overall, providing exploratory p-values (unadjusted log-rank test) for the difference between disease duration categories. This analysis will be repeated for the subgroups presented in Section 5.8.8.

5.5.3.2. Dermatology Life Quality Index (DLQI)

- Change from baseline (week 0) in DLQI score at weeks 116, 164, and 220

The change from baseline in DLQI will be summarized by descriptive statistics using appropriate tabulation. The baseline value, the week 116/164/220 value, and the respective change from baseline value, will be displayed.

A univariate analysis of covariance (ANCOVA) model will be used to test the difference in change from baseline between study groups; the change from baseline being the dependent variable, and former treatment, disease duration, and baseline value of endpoint, as independent variables. A

95% confidence interval for the difference in Least Squares (LS) means and p-value will be calculated based on contrast test statistics. The LS means, the LS mean difference and the standardized mean difference (computed according to Hedges' g), together with the 95% CI and two-sided p-value, will be provided from the ANCOVA model.

- Proportion of subjects who achieve a DLQI score 0/1 and <5 at weeks 116, 164, and 220

The proportion of subjects meeting the response criteria will be displayed in a frequency table providing the number and percentage of subjects per study group (NRI and OC analysis) along with odds ratio (OR), relative risk (RR) and risk difference (RD), and two-sided Wald-type 95% confidence intervals (95% CIs) stratified by 'disease duration'. For single proportions within each study group, unstratified two-sided 95% CIs according to Clopper-Pearson will be calculated. Graphical presentation will be presented by means of bar charts.

The two-group large-sample normal approximation Wald Z-test with Mantel-Haenszel stratum weights for 'disease duration' will be used to compare the proportion of responding subjects among the study groups. The Mantel-Haenszel estimate, the two-sided Wald-type 95% confidence limits, and the test for the difference of proportions will be computed by using Mantel-Haenszel stratum weights (Mantel & Haenszel, 1959) and the Sato variance estimator (Sato 1989).

The respective proportion of subjects will also be given by disease duration category (assessed at baseline, ie, ≤2 years, >2 years) and overall, providing exploratory p-values (unadjusted Chi² test) for the difference between disease duration categories.

Results will also be given for the entire population. In addition, in a modified OC analysis all subjects fulfilling the criteria for re-treatment within the week 116 visit window (ie, PASI>5) will be disregarded. Moreover, the statistical comparison of disease duration categories will be repeated for OC.

5.5.3.3. Body Surface Area (BSA%)

- Change from baseline (week 0) in affected BSA at weeks 80, 104, 116, 140, 164, 188, 212, and 220

The change from baseline in BSA affected by psoriasis will be summarized by descriptive statistics using appropriate tabulation. The baseline value, the values for the respective weeks, and the respective changes from baseline, will be displayed.

A univariate analysis of covariance (ANCOVA) model will be used to test the difference in change from baseline between study groups; the change from baseline being the dependent variable, and former treatment, disease duration, and baseline value of endpoint, as independent variables. A 95% confidence interval for the difference in Least Squares (LS) means and p-value will be calculated based on contrast test statistics. The LS means, the LS mean difference and the standardized mean difference (computed according to Hedges' g), together with the 95% CI and two-sided p-value, will be provided from the ANCOVA model.

5.5.3.4. Nail Assessment in Psoriasis and Psoriatic Arthritis (NAPPA)

- Change from baseline (week 0) in the NAPPA score at weeks 116, 164, and 220, among subjects with nail psoriasis at baseline (week 0)

The change from baseline in the global scores of NAPPA-QOL, NAPPA-PBI, and NAPPA-CLIN will be summarized by descriptive statistics using appropriate tabulation. The baseline value, the

value for the endpoint week of the respective analysis, and the respective change from the baseline value, will be displayed. According to the definition of the global score of NAPPA-PBI, the post-baseline values are already the changes from baseline (there is no baseline value).

No inferential statistical analyses will be performed for global scores of NAPPA-QOL, NAPPA-PBI, and NAPPA-CLIN.

5.5.3.5. Psoriasis Symptom and Sign Diary (PSSD)

- Change from baseline (week 0) in the PSSD Signs and Symptoms aggregate scores at weeks 116, 164, and 220

The change from baseline in the respective PSSD score will be summarized by descriptive statistics using appropriate tabulation. The baseline value, the value for the endpoint week of the respective analysis, and the respective change from the baseline value, will be displayed.

A univariate analysis of covariance (ANCOVA) model will be used to test the difference in change from baseline between study groups; the change from baseline being the dependent variable, and former treatment, disease duration, and baseline value of endpoint, as independent variables. A 95% confidence interval for the difference in Least Squares (LS) means and p-value will be calculated based on contrast test statistics. The LS means, the LS mean difference and the standardized mean difference (computed according to Hedges' g), together with the 95% CI and two-sided p-value, will be provided from the ANCOVA model.

5.6. Additional Analyses

In addition to the efficacy analyses of the study endpoints described above, continuous and binary endpoints related to PASI, DLQI, PSSD, affected BSA, NAPPA, and PSSD, at all scheduled study visits during Study Parts 1, 2 and 3 (Week 0 until Week 116/164/220) will be summarized descriptively (observed cases analysis for continuous endpoints; observed cases analysis and non-responder imputation (after the rule for handling of protocol-prohibited medication/therapy is applied) for binary endpoints). For binary endpoints and the PASI score by visit, data will be presented for the overall population as well.

New analyses that were not pre-planned in the CSP are introduced as follows:

- Proportion of subjects with short (<2 years) and longer (>2 years) disease duration who achieve an absolute PASI score of ≤5 at weeks 116, 164, and 220, per study group

The proportion of subjects responding to treatment will be displayed in frequency tables providing the number and percentage of subjects per study group (NRI and OC analysis) along with odds ratio (OR), relative risk (RR) and risk difference (RD), and two-sided Wald-type 95% confidence intervals (95% CIs) stratified by 'disease duration'. For single proportions within each study group, unstratified two-sided 95% CIs according to Clopper-Pearson will be calculated. Graphical presentation will be presented by means of bar charts.

The two-group large-sample normal approximation Wald Z-test with Mantel-Haenszel stratum weights for 'disease duration' will be used to compare the proportion of subjects with PASI ≤5 among the study groups. The Mantel-Haenszel estimate, the two-sided Wald-type 95% confidence limits, and the test for the difference of proportions will be computed by using Mantel-Haenszel stratum weights (Mantel & Haenszel, 1959) and the Sato variance estimator (Sato 1989).

The proportion of subjects who achieve an absolute PASI score of ≤ 5 will also be given by disease duration category (assessed at baseline, ie, ≤ 2 years, >2 years, <15 months, 15 to 24 months) and overall, providing exploratory p-values (unadjusted Chi² test) for the difference between disease duration categories.

Results will also be given for the entire population. In addition, in a modified OC analysis all subjects fulfilling the criteria for re-treatment within the week 116 visit window (ie, PASI >5) will be disregarded.

- Proportion of subjects with PASI ≤ 5 over time

For each scheduled study visit during Study Parts 1, 2 and 3, the proportion of subjects meeting the response criterion will be displayed in a frequency table providing the number and percentage of subjects, per study group and disease duration category (≤ 2 years, >2 years), and overall. No inferential statistics will be provided.

- PASI values over time in subjects with PASI >0 and ≤ 5 at week 116

For each scheduled study visit during Study Parts 1, 2 and 3, summary statistics for observed values will be provided, restricted to only those subjects who show PASI >0 and ≤ 5 at week 116. Results will be given per study group and disease duration category (≤ 2 years, >2 years), and overall. No inferential statistics will be provided.

- PASI values over time in subjects with PASI ≥ 0 and ≤ 5 at week 116

For each scheduled study visit during Study Parts 1, 2 and 3, summary statistics for observed values will be provided, restricted to only those subjects who show PASI ≥ 0 and ≤ 5 at week 116. Results will be given per study group and disease duration category (≤ 2 years, >2 years), and overall. No inferential statistics will be provided.

- Time to end of the treatment-free period

The time to end of the treatment-free period is defined as time from the visit guselkumab was injected the last time in Study Part 2 to the date of the R0 visit at which re-treatment started, irrespective of PASI assessments. For subjects without re-treatment until the week 116/164/220 visit, the time to end of the treatment-free period will be censored at the date of the week 116/164/220 visit or the date of study termination, whatever comes first. The time to end of the treatment-free period will be computed as:

- Date of R0 visit – Date of last guselkumab injection in Study Part 2, if the subject started re-treatment,
- First date of (week 116/164/220 visit or study termination) – Date of last guselkumab injection in Study Part 2, if the subject did not start re-treatment.

The time to end of the treatment-free period will be analyzed using the Kaplan-Meier product limit method and Cox proportional hazards model. Summary tables will provide counts and percentages by study group and total, the median time-to-event with 95% confidence intervals (CI), and the hazard ratio (including 95% CI and the p-value calculated from Cox-regression with the factors 'study group' and 'disease duration'). The survival curves will also be displayed graphically (for all subjects, and additionally only for subjects previously treated with guselkumab q8w). Time-to-event analyses of binary endpoints will be performed on the observed cases only after the rule for

handling of protocol-prohibited medication/therapy is applied. (ie, missing data will not be replaced for time-to-event analyses).

Time to end of the treatment-free period will also be evaluated by disease duration category (assessed at baseline, ie, <15 months, 15 to 24 months, \leq 2 years, $>$ 2 years) and overall, providing exploratory p-values (unadjusted log-rank test) for the difference between disease duration categories. A Kaplan-Meier graphic will show the time to end of the treatment-free period for categories <15 months, 15 to 24 months, and $>$ 2 years.

The analyses will be repeated for the subgroups presented in Section 5.8.8.

- Proportion of subjects with DLQI values falling in quality-of-life categories

DLQI values, if available within a visit window and if not after start of a prohibited medication, will be assigned to one of the categories presented in the following table:

Table 3 – DLQI Categories

DLQI Score	Meaning of Category
0 to 1	Psoriasis has no effect on quality of life
2 to 5	Psoriasis has a mild effect on quality of life
6 to 10	Psoriasis has a moderate effect on quality of life
11 to 20	Psoriasis has a severe effect on quality of life
21 to 30	Psoriasis has a very severe effect on quality of life

For selected study visit during Study Parts 1 (baseline, week 28), 2 (weeks 52 and 68) and 3 (weeks 80, 92, 104, 116, 140, 164, and 220), the proportion of subjects in each category will be displayed in a frequency table providing the number and percentage of subjects, per study group and disease duration category (\leq 2 years, $>$ 2 years), and overall. No inferential statistics will be provided. Percentages will be based on the available number of subjects with non-missing data per visit.

Update before the final analysis:

- An additional frequency table will be provided for the number and proportion of subjects starting re-treatment after week 68 to week 116, after week 116 to week 164, and after week 164 to week 220; proportions will also be broken down by disease duration subgroups.
- The proportion of subjects with PASI or DLQI response by visit will be evaluated twice, first using the NRI approach and second the OC modified approach (applied to all visits after week 68).
- In addition, all efficacy scores (PASI, DLQI, PSSD, BSA, and NAPPA) by visit and changes from baseline will be presented only for visits with PASI $<$ 5 (OC modified, applied to all visits after week 68), with subgroups A and B (see Section 5.8.8).
- The endpoints PASI values over time in subjects with PASI $>$ 0 and \leq 5 at week 116 and PASI values over time in subjects with PASI \geq 0 and \leq 5 at week 116 will not be evaluated for the Week 220 analysis.
- Proportions of subjects with DLQI response (0/1; $<$ 5) by visit will be given by subgroups A and B only.
- DLQI categories will not be evaluated for the Week 220 analysis.

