5.8.8. Definition of Subgroups

Subgroup analyses are planned to be performed for the major secondary endpoints in study groups **3a** and **3b** as well as for other endpoints:

- Proportion of subjects who achieve an absolute PASI score of 0, ≤ 1 and < 3 at week 116/164/220
- Proportion of subjects who retain disease control (PASI < 3) from week 68 on
- PASI values over time
- Time to end of the treatment-free period
- Proportion of subjects who achieve a DLQI score 0/1 or < 5 over time.

All subgroup analysis will be performed unstratified, ie, without use of 'disease duration' as stratification factor in the exploratory inferential statistical analysis. The following subgroups will be defined:

- A: Disease duration at baseline
 - ≤ 2 years
 - > 2 years
- B: Disease duration at baseline for subjects with short disease duration (SDD; ≤ 2 years) only
 - < 15 months
 - 15 to 24 months
- C: Age at baseline
 - < 45 years
 - ≥ 45 to 65 years
 - > 65 years
- D: BMI at baseline
 - normal (≤ 25 kg/m²)
 - overweight ($> 25 - 30$ kg/m²)
 - obese (> 30 kg/m²)
- E: Body weight at baseline
 - ≤ 90 kg
 - > 90 kg
- F: PSO-pretreatment (for hierarchical categorization see section 6.5)
 - No prior therapy
 - Topical therapy
 - Phototherapy
 - Non-biologic systemic therapy
 - Biologic therapy
- G: PSO-pretreatment with biologics
 - Biologic naïve (including subjects without PSO-pretreatment)
 - 1 or more biologics.

Based on the week 68 visit (nominal, not necessarily within the visit window), the following subgroups will be defined, if PASI was assessed:

- H: PASI score at week 68
 - PASI =0 at week 68
 - PASI >0 at week 68.

For these subgroups the following endpoints will be analyzed:

- Proportion of subjects who achieve an absolute PASI score of 0, ≤ 1 and < 3 at week 116/164/220
- Proportion of subjects who achieve an absolute PASI score < 3 and ≤ 5 by visit
- PASI values over time

- Time to end of the treatment-free period
- Proportion of subjects who achieve a DLQI score 0/1 and <5 over time
- Proportion of subjects with DLQI values falling in quality-of-life categories.

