6.2. Appendix 2 Changes to Protocol-Planned Analyses

No important changes from the planned analyses specified in the protocol and its amendments were applied.

However, the time point of analyses is changed slightly. While the CSP states that “interim analyses are planned after all subjects have completed their visit at week 116 (or at week 144 in case of subjects entering the re-treatment arm in week 116) and at week 164 (or at week 192 in case of subjects entering re-treatment arm in week 164). The final analysis will be performed after all subjects have completed their visit at week 220 (or at week 248 in case of subjects entering the re-treatment arm in week 220)”, it was decided to split the analyses of group 3a/3b subjects and the analyses of group 3c subjects (re-treatment phase). By this, the results for the week 116/164/220 analyses of study groups 3a and 3b will be available as soon as possible. A separate SAP will be written for the analysis of the re-treatment phase that will include – beneath the group 3c – also the analysis of study group 2d (subjects who entered the re-treatment phase already in study part 2).

In addition, some new analyses have been added to the evaluation; see section 5.6 for details.

The initial SAP, prepared before the Dry-run meeting for the first interim analysis (week 116), was updated several times during the course of the study:

- Changes introduced before the Week 116 analysis:
 - The windows for the week 28, 68, 116, 164 and week 220 visits are expanded.
 - For LOCF, the earliest visit used for carrying forward is the week 68 visit.
 - Statistical testing for binary endpoints is also performed for the OC analysis.
 - For binary endpoints, a modified OC analysis is done to exclude visits with PASI>5.
 - Subgroups are compared by statistical testing.
 - The analysis of adverse events excluded AEs starting on the day of the R0 visit.
- Change introduced before the Week 164 analysis:
 - Demographic data are displayed separately for each subgroup.
- Changes introduced before the Week 220 analysis:
 - The subgroups C to H are not evaluated for the analysis of PASI and DLQI response.
 - For the time-to-event endpoints, subgroups I to H are added.
 - All efficacy endpoints (PASI, DLQI, PSSD, BSA, and NAPPA scores and changes from baseline) by visit are presented only for visits with PASI < 5 (OC modified), with subgroups A and B.
 - PASI and DLQI response by visit are evaluated for NRI and OC modified.

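### Part 3 SAP: the modified observed-case analysis of PASI ≤5 leaves out exactly the non-responders, so it is 100% at week 116 and, on the final-analysis wording, at every visit after week 68

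*SAP*

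**What the plan says.** All references are to the Study Part 3 SAP unless stated otherwise.

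- **Endpoint.** Section 5.6 introduces, as an analysis not planned in the protocol, the proportion of subjects "who achieve an absolute PASI score of ≤5 at weeks 116, 164, and 220, per study group". It is reported by NRI and OC, with odds ratio, relative risk, risk difference, a Mantel-Haenszel weighted Wald test with Sato variance, and Chi² tests between disease-duration categories. A by-visit version is listed separately: "Proportion of subjects with PASI ≤ 5 over time".
- **Modified OC rule.** The same item in 5.6 adds that "in a modified OC analysis all subjects fulfilling the criteria for re-treatment within the week 116 visit window" (glossed there as PASI >5) are disregarded.
- **General form of the rule.** Appendix 2 (6.2), under changes made before the week 116 analysis: "For binary endpoints, a modified OC analysis is done to exclude visits with PASI>5".
- **Final analysis.** The update at the end of 5.6 has PASI and DLQI response by visit evaluated twice, "first using the NRI approach and second the OC modified approach (applied to all visits after week 68". Appendix 2 repeats this for the week 220 analysis.
- **Scores.** The same update restricts the efficacy scores with a different cut-off: "by visit and changes from baseline will be presented only for visits with PASI $<$ 5 (OC modified, applied to all visits after week 68".
- **End of follow-up.** Section 5, Note 2, evaluates relapsing subjects only up to R0, the visit at which PASI >5 is seen.

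**The concern.** Section 1.1.2 defines loss of disease control as PASI >5, so PASI ≤5 means that control has not been lost. An analysis that removes PASI >5 before counting PASI ≤5 takes out every failure and nothing else. R0 is the last visit at which a relapsing subject is evaluated in Part 3, and it is the one that records the failure. The rule deletes it.

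The same sentence follows the endpoints PASI 0, ≤1 and <3 (5.4.3), PASI 75/90/100 (5.5.3.1) and DLQI response (5.5.3.2). There it conditions on not having relapsed, but the proportion can still vary. Only for PASI ≤5 does it fix the answer in advance, and nothing in the SAP exempts that endpoint.

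At stake is the usefulness of one set of tables. A constant 100% says nothing about 3a versus 3b or about short versus long disease duration, and without a warning it could be read as complete control among the subjects still observed.

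**Working it through.** The plan gives no figure for this analysis, so there is none to reproduce. The check is structural.

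**1. The proportion at one visit.** Let *k* be the number observed with PASI ≤5 and *f* the number observed with PASI >5.

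- Ordinary OC: k / (k + f).
- Modified OC: the denominator is (k + f) − f = k and the numerator is k, so the result is k/k = 1 for any k > 0.

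**2. Numerical confirmation.** Assumptions: 137 subjects per group in two disease-duration strata (55 and 82), and four pairs of true control rates. Counts were simulated, and the Mantel-Haenszel risk difference (RD) was taken as second group minus first.

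| Ordinary OC, group 1 vs group 2 | RD (points) | Z | Modified OC | RD | Sato variance |
|---|---|---|---|---|---|
| 86.9% vs 88.3% | +1.5 | 0.37 | 100% vs 100% | 0 | 0 |
| 91.2% vs 54.7% | −36.5 | −7.47 | 100% vs 100% | 0 | 0 |
| 64.2% vs 8.8% | −55.5 | −11.64 | 100% vs 100% | 0 | 0 |
| 16.8% vs 16.8% | 0.0 | 0.00 | 100% vs 100% | 0 | 0 |

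The 100% does not depend on the assumed sizes or rates. If a Clopper-Pearson interval were attached, its lower 95% limit would be 0.025^(1/k), which depends only on how many subjects were kept. In the second row that gives 0.971 for k = 125 and 0.952 for k = 75.

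**3. Which visits are affected.**

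| Place | Scope of the exclusion | PASI ≤5 result |
|---|---|---|
| 5.6, modified OC sentence | PASI >5 in the week 116 window | 100% at week 116; weeks 164 and 220 can vary |
| 6.2, before the week 116 analysis | Visits with PASI >5, binary endpoints | 100% at any visit to which it is applied |
| 5.6, update before the final analysis | OC modified at all visits after week 68, PASI response by visit | 100% at each of those visits |

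For the literal week 116 scope: if 68 subjects are kept and 41 of them have PASI ≤5 at week 164 (assumed), the result is 41/68 = 60.3%, which is not degenerate. Week 116 therefore follows from the modified OC sentence alone. The other visits need the update in 5.6 and Appendix 2 read together.

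**4. Cut-off.** The binary rule drops PASI >5, while the score rule keeps only PASI <5. A score of exactly 5 is possible under the protocol's formula (Attachment 2), for example 0.4 × 6 × 2 + 0.1 × 2 × 1 = 4.8 + 0.2 = 5.0. Such a visit is kept in one set of tables and dropped from the other. With either cut-off, everyone kept has PASI ≤5, so the 100% stands.

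**The case against.** The strongest reply is that little information is lost. At weeks 116, 164 and 220, Section 5.6 still requires NRI and ordinary OC for PASI ≤5, with tests. Loss of control is analysed by Kaplan-Meier and Cox models (5.5.1.1, 5.5.3.1), the treatment-free period likewise (5.6), and re-treatment starts are tabulated by period and disease duration. Section 5.1 makes all of Part 3 exploratory. This stands, and it sets the severity.

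A second reply concerns scope. The update in 5.6 speaks of PASI response without naming PASI ≤5, and the update in 5.8.8 lists PASI response as 0, ≤1, <3 and retained control. Against this, 5.6 itself describes PASI ≤5 over time as meeting a response criterion, and Appendix 2 refers to binary endpoints without exception. The extension beyond week 116 is the natural reading, but it remains an inference.

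A reader might infer more than the documents support:

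- **A gap of 16.8% versus 100%.** Section 4.5 of the overall safety SAP counts 227 of 273 withdrawal subjects as re-treated after PASI >5, so NRI at week 220 is at most 46/273 = 16.8%. Most of that gap is NRI against any OC analysis, because relapsers' data end at R0. If 46 subjects were controlled at week 220 and 5 relapsed at that visit (assumed), ordinary OC would be 46/51 = 90.2%. The effect of the exclusion is that figure against 100%, and the documents do not supply it.
- **Undefined by-visit p-values, or lost power.** Section 5.6 orders no inferential statistics for PASI ≤5 over time. At week 116 a test on the modified set would be 0/0, but Appendix 2 lists testing for the OC analysis and the modified OC analysis as separate items, so a test of the latter is not clearly ordered.
- **Empty subgroup tables.** Section 5.8.8 lists "Proportion of subjects who achieve an absolute PASI score < 3 and ≤ 5 by visit" for subgroup H, but the same section uses NRI for binary endpoints in subgroups.

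**Conclusion.** The point holds in limited form. At week 116 the modified OC proportion for PASI ≤5 is 100% in 3a, in 3b and in each disease-duration category by construction, with no assumption beyond at least one subject being kept. For the other visits after week 68, the table planned as OC modified for the final analysis is also a constant 100%, provided that PASI ≤5 counts as a PASI response in the update to 5.6. The week 116 wording does not by itself make weeks 164 and 220 degenerate, and the two scopes conflict.

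The distance between ordinary and modified OC at a visit depends on how many subjects show PASI >5 at that visit, which the documents do not report. No confirmatory conclusion is touched. Severity: minor.

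**What to change.** In the Part 3 SAP, Sections 5.6 and 6.2:

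1. Drop the modified OC analysis for PASI ≤5, both at weeks 116, 164 and 220 and by visit.
2. In the week 220 by-visit tables, show the ordinary observed-case proportion next to NRI, keeping the R0 visit with PASI >5 in the denominator as a non-response. Add a footnote that subjects who relapsed earlier are absent from any observed-case denominator, so this proportion is not retention since week 68.
3. For the endpoints where modified OC is kept, state one visit scope (the week 116 window, or all visits after week 68) and one cut-off (PASI >5 excluded, or only PASI <5 kept), and use both consistently for binary endpoints and scores.

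Cost: a sentence or two in the SAP, one denominator flag in the by-visit response program and one set of tables dropped or re-run. No new data are needed.
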